3.5. Other Analyses

Not applicable for the synoptic CSR.

3.5.1. Other Variables and/or Parameters

Not applicable for the synoptic CSR.

3.5.2. Subgroup Analyses

Not applicable for the synoptic CSR.

3.6. Interim Analyses

No interim analysis is planned for this study but the database lock for the Maintenance Study Protocol 0157 will occur prior to the end of the study.

Blinding

Bias in safety evaluation will be minimized through partial dose-blinding. The dose will be blinded however it will be known to all parties that all subjects are on TD-1473. In the case of subjects completing the Maintenance Study, the investigator will have firsthand observation of remission status but initially remain blinded to the precedent dose assignment in Maintenance.

Thus, the specific dose assignment in LTS for Maintenance completers in remission will not be known to investigator, Sponsor, or subject. The dose assignment in LTS for subjects who enter without completing the Maintenance Study or who complete the Maintenance Study but are not in remission is also partially dose-blinded, as the consent form will include the treatment assignment scheme and all subjects will be assigned to an escalated dose from their preceding Maintenance TD-1473 dose. Once the database lock and unblinding have occurred in the precedent Maintenance Study Protocol 0157, the prior dose assignment may be disclosed.

3.6.1. Data Monitoring Committee

[REDACTED]

5. SUPPORTING DOCUMENTATION

5.1. Appendix 1: Changes to Protocol-Planned Analyses

The protocol-planned efficacy analyses are not required for the synoptic CSR.

5.2. Appendix 2: Data Conventions and Transformations

5.2.1. Derived and Transformed Data

5.2.1.1. Study Day

If the date of interest occurs on or after the first dose/randomization date, then study day will be calculated as (date of interest – date of first dose/randomization) + 1.

If the date of interest occurs prior to the first dose/randomization date, then study day will be calculated as (date of interest – date of first dose/randomization).

There is no Study Day 0.

5.2.1.2. Change from Baseline

Change from baseline is calculated as (postbaseline result – baseline result).

Percent change from baseline is calculated as (change from baseline/baseline result) × 100 or equivalently as 100 × (postbaseline value/baseline value - 1).

If either the baseline or the postbaseline result is missing, the change from baseline and percentage change from baseline values are missing.

5.2.1.3. BMI

BMI is calculated as:

$$BMI (kg / m^2) = \frac{weight (kg)}{height (m)^2}.$$

5.2.2. Missing Data Imputation

5.2.2.1. Missing/Incomplete AE/Start Date

Imputation of dates with missing day and/or month is only applied to TEAEs. TEAE start dates with missing day or month will be imputed as follows:

- If day and month are missing but year is available, then the imputed day and month will be 01 Jan [with a time of 00:00 if applicable] or first study drug dose date if they have the same year, whichever is later (because TEAE onset is not expected prior to administration of study treatment)
- If day is missing but the month and year are available, then the imputed day will be the first day of the month [with a time of 00:00 if applicable] or the first study drug dose date if they have the same month and year, whichever is later.

5.2.2.2. Missing/Incomplete AE/Medication End Date/Time

Imputation of dates with missing day and/or month is only applied to TEAEs when AE duration is calculated. TEAE end dates with missing day or month will be imputed as following:

- If day and month are missing but year is available, then the imputed day and month will be 31 Dec [with a time of 23:59 if applicable] or the date and time of last study drug dose if they have the same year, whichever is earlier
- If day is missing but the month and year are available, then the imputed day will be the last day of the month [with a time of 23:59 if applicable] or the date and time of the last study dose if they have the same month and year, whichever is earlier.

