### 8.6.1. Adverse Event Data

Adverse events will be coded using the Medical Dictionary for Regulatory Activities (MedDRA®). Summaries will present by system organ class (SOC), preferred term (PT), and severity, the number and percentage of subjects reporting each observed event.

A treatment-emergent adverse event (TEAE) is defined as any AE with a recorded start date on or after the date of the first dose of LTS study drug up through 4 weeks after the last dose of study drug. Treatment-emergent status of AEs with a partial start date will be determined using available date information. If the available date information is inconclusive or no date information was recorded, the AE will be classified as LTS treatment-emergent.

All TEAEs will be listed by subject, and a separate listing of AEs classified as not LTS treatment-emergent (i.e., ongoing at entry) will be provided. Numbers of subjects who experienced TEAEs will be summarized overall and by arm. TEAEs will also be summarized by relationship to treatment (study drug) and severity, and by duration of exposure categories to be specified in the SAP.

A listing will be provided for all subjects who experience an SAE. Listings will also be provided for subjects who discontinued study treatment because of AEs, subjects who temporarily interrupted study treatment because of AEs, and subjects who experienced AESIs.

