1. INTRODUCTION

This statistical analysis plan (SAP) outlines the planned summarization and analysis of clinical data collected in the long-term safety (LTS) study of Protocol 0164 for TD-1473. Specifications for tables, figures, and data listings are contained in a separate document.

The results of the planned analyses will be presented in a synoptic clinical study report (CSR) which will include analyses of study subject data and safety endpoints. Inferential statistical tests will not be performed. The protocol-planned efficacy analyses will be excluded as they are not necessary for a synoptic CSR.

The 0164 study was terminated early due to lack of efficacy in the 0157 study, for all subjects the date of last dose occurred by 09SEP2021 and the end of study visit by 11OCT2021.

The analysis of pharmacokinetics data (derivation and summarization of individual PK parameters) is outside the scope of this document and is not addressed here.

This document describes the a priori plan for analysis. Any substantive modification to this analysis plan will be identified in the CSR.

Information in the appendices to the SAP are not considered a formal section of the signed SAP.

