3.4.2. Adverse Events

Adverse events (AEs) will be coded to the preferred terms (PT) of the Medical Dictionary for Regulatory Activities (MedDRA®). Summaries will be presented by system organ class (SOC), preferred term, and severity and/or relatedness, the number and percentage of subjects for whom events were reported.

Adverse events (AEs) are recorded from signing of the informed consent form through the final follow-up assessment. Adverse events observed prior to first dose are non-treatment emergent.

Treatment emergent adverse events are defined as follows:

- TEAEs are AEs with onset on or after the first initiation of study drug up to the date of last dose of study drug + 28 days.

Only treatment-emergent AEs will be summarized in the tables. A listing of all TEAEs by subject will be provided.

An AE will be considered a treatment emergent serious AE (TESAE) if it is a TEAE that additionally meets any SAE criteria.

If more than 1 AE is coded to the same preferred term for the same subject, the subject will be counted only once for that preferred term using the most severe and most related occurrence for the summarizations by severity and by relationship to study drug.

Summary tables will also be provided for subjects with:

- TESAEs by SOC and PT
- TEAEs leading to discontinuation of study drug by SOC and PT
- TEAEs leading to temporary interruption of study drug by SOC and PT

- TEAEs by severity and by SOC and PT
- Drug related TEAEs by severity and by SOC and PT

Listings of all AEs, SAEs, AEs resulting in death, and AEs leading to discontinuation by subject will be presented.

An overall summary of adverse events will also be presented and will include the following summary lines: Any AE, Moderate or Severe AEs, AEs Related to Study Drug, Moderate or Severe AEs Related to Study Drug, Serious AEs, Serious AEs Related to Study Drug, AEs Leading to Premature Study Drug Discontinuation, AEs Leading to Temporary Interruption of Study Drug, and Deaths During Study.

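### SAP 5.2.2.2 caps partial TEAE end dates at the last dose, so an event starting in the following 28 days can be given an end before its onset

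*SAP*

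**What the plan says.** SAP section 5.2.2.2 (Appendix 2) has two rules for incomplete TEAE end dates. If only the year is known, the end is 31 December "or the date and time of last study drug dose if they have the same year, whichever is earlier". If month and year are known, it is the last day of the month "or the date and time of the last study dose if they have the same month and year, whichever is earlier". The scope is narrow: "Imputation of dates with missing day and/or month is only applied to TEAEs when AE duration is calculated".

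SAP section 3.4.2 counts an AE as treatment-emergent if it starts on or after first dose and "up to the date of last dose of study drug + 28 days". Protocol section 8.6.1 agrees, "up through 4 weeks after the last dose of study drug". Collection covers the same period: "Adverse events (AEs) are recorded from signing of the informed consent form through the final follow-up assessment". Protocol section 7.5 goes further. An event is followed to the follow-up visit or until it has resolved or stabilised, taking the longer of the two.

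The start-date rule in SAP section 5.2.2.1 sets the earliest imputed start at first dose. It makes no link between the start and the imputed end.

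**The concern.** The TEAE definition deliberately takes in events that begin after dosing has stopped, and follow-up lets events resolve after dosing has stopped. The end-date rule assumes the opposite, because it never lets an imputed end fall after the last dose when the two share the recorded year or month. Two faults follow:

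- A TEAE with onset after the last dose can be given an end date before its onset, which is impossible.
- A TEAE that began on treatment and continued past the last dose can be cut off at the last dose.

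A programmer who applies the text literally would produce zero or negative durations for the first kind and shortened durations for the second. Safety is the study's primary objective, so a rule for deriving AE duration should at least return possible values.

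**Working it through.** The plan states no figure on this point, so there is nothing to reproduce. The check applies the two rules to the plan's own dates.

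**Inputs**
- TEAE onset window: to last dose + 28 days (SAP 3.4.2).
- End-date rules: SAP 5.2.2.2, both bullets.
- Dates: "for all subjects the date of last dose occurred by 09SEP2021 and the end of study visit by 11OCT2021" (SAP section 1). The examples take 09SEP2021 as last dose and 11OCT2021 as EOS.
- Duration = end - start + 1. This is an assumption, since the SAP gives a formula for treatment duration (3.4.1) but none for AE duration. That an end precedes its onset does not depend on it.

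**Rule.** Imputed end = min(period end, last dose) if the last dose falls in the recorded period; otherwise the period end.

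| Onset | Recorded end | Imputed end | Duration (days) |
|---|---|---|---|
| 15SEP2021 | SEP2021 | min(30SEP, 09SEP) = 09SEP2021 | 9 - 15 + 1 = -5 |
| 20SEP2021 | 2021 | min(31DEC, 09SEP) = 09SEP2021 | 9 - 20 + 1 = -10 |
| 05SEP2021 | SEP2021 | min(30SEP, 09SEP) = 09SEP2021 | 9 - 5 + 1 = 5 |
| 01OCT2021 | OCT2021 | 31OCT2021 (cap not triggered) | 31 - 1 + 1 = 31 |
| 05JAN2021 | 2021 | min(31DEC, 09SEP) = 09SEP2021 | 252 - 5 + 1 = 248 |

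The third event could have lasted up to 30 - 5 + 1 = 26 days. In the last row, 09SEP is day 243 + 9 = 252 of the year.

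**How much of the 28-day window is affected**
- Year-only end date in the year of the last dose: an onset k days after the last dose has duration 1 - k. For k = 1 to 28 this runs from 0 to -27, so all 28 onset days give an end before onset.
- Month-and-year end date in the onset month, last dose 09SEP2021: onsets on 10 to 30 September fail, which is 30 - 9 = 21 of 28 days. For the other 28 - 21 = 7 (1 to 7 October) the cap does not apply.
- Over all last-dose dates from 01JAN2021 to 09SEP2021, the year-only count is always 28 of 28. The month-and-year count runs from 0 (last dose on the last day of a month) to 28.

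**With the cap moved to 11OCT2021** (assuming no later contact) **and a floor at onset**
- 15SEP / SEP2021: end 30SEP2021, 30 - 15 + 1 = 16 days.
- 20SEP / 2021: end 11OCT2021, 11 days in September + 11 in October = 22 days.
- 05SEP / SEP2021: end 30SEP2021, 26 days.
- 01OCT / OCT2021: end 11OCT2021, 11 days.
- 05JAN / 2021: end 11OCT2021, day 273 + 11 = 284, so 284 - 5 + 1 = 280 days.

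No imputed end precedes its onset.

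**The case against.** The strongest objection is that no visible output uses the rule. It operates only when AE duration is calculated. The AE outputs in SAP sections 3.4, 3.4.2 and 3.4.2.1 are counts, percentages and listings by class, term, severity, relatedness, seriousness and AESI category, and none mentions duration. TEAE status depends on the start date alone. The rule also sits in an appendix that SAP section 1 places outside the formally signed plan. All of this stands, and it keeps the point minor. It does not remove the point, because the SAP has written a rule for a derived quantity and the rule can return impossible values. The table and listing specifications are in a separate document not available here.

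Three stronger readings are tempting and are not supported:

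- A reader might infer that the error always favours the drug. It does not. The rule takes the latest date up to the cap, so an event that truly ended before the last dose can be lengthened. The January event above is given 248 days even if it lasted three. A negative duration is a visible data error rather than a flattering one. Every subject receives TD-1473, the rule is the same at each dose, and no inferential tests are planned.
- A reader might infer that every derived AE duration is wrong. The fault needs a partial end date in the same year, or month and year, as the last dose, and an event that starts or continues after that dose. Complete dates are unaffected.
- A reader might infer from the heading of section 5.2.2.2 that medication end dates carry the same cap. The text below it deals with TEAEs only, so there is no medication cap to correct.

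It is also fair to object that EOS alone is not a safe replacement cap, since protocol section 7.5 allows follow-up beyond that visit. That stands and shapes the fix.

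**Conclusion.** The rule is wrong as written, in a small way. It contradicts the SAP's own TEAE window, and no other section repairs it. For a TEAE that starts after the last dose, a year-only end date in the year of that dose always produces an end before onset. A month-and-year end date does so when the end month is the month of the last dose. A TEAE that continues past the last dose is truncated under the same conditions.

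The consequence is limited to any AE duration that is derived. Incidence, severity and AESI counts do not change. The number of partial end dates is not in the documents, so the number of affected records cannot be estimated. The durations quoted rest on the assumed formula end - start + 1; the impossible ordering of dates does not.

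**What to change.** In both bullets of SAP section 5.2.2.2, replace the last-dose cap with the later of the study exit (EOS) date and the date of last contact. Add that the imputed end may not be earlier than the AE onset date.

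Taking the later of the two dates covers events followed beyond EOS. The date of last contact is already in the disposition listing (SAP 3.2.2). The year-only medication start rule in SAP 5.2.2.3 already uses study exit as its limit, so the change also brings the two rules closer together. Medication end dates need no change under this point.

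The revised rule still takes the longest reading compatible with the recorded date, so some short events remain overstated (the January example moves from 248 to 280 days). It removes the impossible ends and the cut at the last dose, but not the uncertainty of a partial date.

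The cost is a short edit to two bullets and the matching program line, with no new data and no change to any table the SAP specifies. If durations have already been derived, the records to recheck are TEAEs with a partial end date imputed to the last-dose date.

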5.2.2.3. Missing/Incomplete Start for Medication

To determine whether medications were used prior to initiation of dosing and whether they were used after initiation of dosing, missing or partial dates for medications will be imputed according to the following rule:

Missing medication start date/time:

- If day and month are missing but year is available, then the imputed day and month will be 31 Dec [with a time of 23:59 if applicable] or the study exit date if they have the same year, whichever is earlier.
- If day is missing but the month and year are available, then the imputed day will be the first day [or 1 minute after midnight if applicable] of the month or the first dose date if they have the same month and year, whichever is later.
- If day, month and years are completely missing, impute as date and time of first dose if 1) end date is not missing and occurs on and after date of first dose, or 2) end date is missing but marked as “ongoing”.

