3.2.6. Prior/Concomitant Medications

Prior medications include all medications taken prior to the first dose of study drug, regardless of when they were stopped. Concomitant medications include all nonstudy medications that the subject was taking prior to the Day 1 visit that were ongoing at the visit, in addition to all medications with a start date on or after the first dose date and no later than the last dose date + 28 days. Medications with a start date after the last dose date + 28 days will be included in a listing of concomitant medications with a flag.

Recorded prior and concomitant medication names will be mapped according to [REDACTED]

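### The SAP imputes a year-only medication start to the latest possible date, so some drugs taken before first dose or started on treatment are misclassified

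*SAP*

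**What the plan says.** SAP 5.2.2.3 gives the purpose of its rules: "To determine whether medications were used prior to initiation of dosing and whether they were used after initiation of dosing". Three rules for incomplete start dates follow:

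- Year only: 31 December, "or the study exit date if they have the same year, whichever is earlier".
- Month and year: the first of the month, "or the first dose date if they have the same month and year, whichever is later".
- Nothing known: the first dose date, provided that the end date is on or after first dose, or is missing with the drug marked as ongoing.

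SAP 3.2.6 counts as prior any drug taken before first dose. A drug is concomitant by either of two routes. The subject was "taking prior to the Day 1 visit that were ongoing at the visit", or the drug is among the "medications with a start date on or after the first dose date and no later than the last dose date + 28 days". Later starts are not dropped: "Medications with a start date after the last dose date + 28 days will be included in a listing of concomitant medications with a flag".

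SAP 5.2.2.1 treats a year-only start of a treatment-emergent adverse event the other way: 1 January, or the first dose date if in the same year, whichever is later.

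Protocol 6.3.6 and Table 1 place the End of Study (EOS) visit 4 weeks after last dose, with a window of 3 days early to 5 days late. SAP Section 1 says that for all subjects "the date of last dose occurred by 09SEP2021 and the end of study visit by 11OCT2021".

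**The concern.** The rules do not run in a consistent direction. If the month is known, the start goes to the earliest plausible date. If nothing is known, it goes to first dose, subject to the condition above. If only the year is known, it goes to the last date possible. No reason is given. A form built on 31 December and the earlier of two dates is the form that SAP 5.2.2.2 uses for end dates. It may have been carried over from there, but the documents do not say so.

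The rule exists to separate use before first dose from use after it. Pushing a start to year end or to exit works against that for any drug whose recorded year is also the year of first dose. At stake are the prior and concomitant labels in a study whose primary objective is safety, and the accuracy of the flag for drugs started after the window.

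**Working it through.** The plan states no figure to reproduce, so the check is date arithmetic on its rules.

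**Inputs.** F is the first dose date, L the last dose date, E the study exit date and Y the recorded start year. E is taken as the EOS visit; this is an assumption, because the SAP does not define study exit date. The EOS window gives E = L + 25 to L + 33 (28 - 3 to 28 + 5), which is 9 permitted days.

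**Formulas.** Imputed start S = min(31 Dec Y, E) if E falls in year Y; otherwise S = 31 Dec Y. The drug is concomitant by start date if F ≤ S ≤ L + 28.

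**1. Direction of the rules**

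| Date and what is known | Rule | Direction |
|---|---|---|
| Medication start, month and year | later of first of month and F | earliest plausible |
| Medication start, year only | earlier of 31 Dec and E | latest plausible |
| Adverse event start, year only | later of 1 Jan and F | earliest plausible |

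**2. Drug started on treatment, recorded with the exit year.** Here S = E unless 31 December comes first.

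- E on days 25 to 28: S is inside the window (4 of 9 permitted days).
- E on days 29 to 33: S is outside (5 of 9), unless 31 December is no later than L + 28, that is, unless L is 3 December or later.

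Taking every last-dose date in 2020 and a drug recorded as 2020, S is outside the window for 0 of 366 dates at each of days 25 to 28, and for 337 of 366 (92%) at each of days 29 to 33. The other 29 are 3 to 31 December. These count calendar dates; they do not estimate how often the error occurs.

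**3. Illustration with the SAP's latest dates, joined as if one subject.** L = 09SEP2021, so L + 28 = 07OCT2021. E = 11OCT2021, which is 21 + 11 = 32 days after L. For a drug recorded as 2021, S = min(31DEC2021, 11OCT2021) = 11OCT2021. That is 32 - 28 = 4 days past the window, and the drug is flagged as a late start. With E = 07OCT2021 (day 28) the same drug stays inside, although its start is still placed 28 days after last dose.

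**4. Drug taken and stopped before first dose.** Assume F = 01JUN2021, drug taken from February to 30APR2021, and start recorded as 2021. With E = 11OCT2021, S = 11OCT2021. This is after F, so the drug is not prior, and after its own stop date. It is also flagged as a late start. With E = 07OCT2021 it would count as concomitant by start date. Both results are wrong.

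**5. Where the label is unaffected.** A drug recorded as 2020, with F = 01JUN2020 (assumed), L = 09SEP2021 and exit in 2021, gets S = 31DEC2020 and stays concomitant. A recorded year before the year of first dose gives S before F, so the drug is correctly prior.

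**6. Test of the adverse event convention, max(1 Jan Y, F).** With L = 09SEP2021 and a drug recorded as 2021, an assumed F of 02NOV2020 gives 01JAN2021, and an assumed F of 01MAR2021 gives 01MAR2021. Both are inside the window on all 9 permitted days. For the drug in step 4, however, it gives max(01JAN2021, 01JUN2021) = 01JUN2021, still not before first dose and still after the stop date. Changing the convention alone is not enough.

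**The case against.** The case for leaving the rule alone is substantial. Protocol 6.4.1.9 requires start and stop dates, and Protocol Table 1 has medications reviewed at every visit, so year-only starts of new drugs should be uncommon. The study was terminated early, reports through a synoptic CSR and runs no inferential tests. SAP Section 1 says that the appendices are not a formal section of the signed plan. All of this limits the consequence. It does not remove the error, because the documents show no other rule for partial medication starts.

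Three stronger readings are tempting, and the documents do not support them.

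- A reader might infer that every year-only start in the exit year drops out of the concomitant set. Every such start is dated late (to exit, or to 31 December if that is earlier), but at the nominal EOS day and up to 3 days before it the drug stays inside the window. An exit before EOS would also keep it inside.
- A reader might infer that drugs taken throughout treatment, such as steroids or rescue medication continued from Maintenance, are lost. A drug documented as ongoing at Day 1 qualifies by the other route in SAP 3.2.6, and Protocol 6.4.1.2 has concomitant medications reviewed on Day 1. Drugs outside the window remain in the listing; what is wrong is their flag.
- A reader might infer that adverse event findings are distorted because a drug appears to start after an event it may explain. The SAP shows no medication-by-event analysis, and SAP 3.1 lists individual data as measured.

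The dates in step 3 are also study-wide upper limits. The SAP does not say that any one subject had both.

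The adverse event rule is not a perfect model either. Its stated reason, that onset is not expected before treatment, does not hold for medications. That objection stands and shapes the fix.

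**Conclusion.** The year-only rule is wrong as written. It takes the latest plausible date, against the month-known bullet and SAP 5.2.2.1, and has no cap at the recorded end date. It misclassifies two groups:

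- drugs taken and stopped before first dose in the same calendar year, which lose their prior status;
- drugs newly started on treatment and recorded only with the exit year, which are wrongly flagged when the imputed start is more than 28 days after last dose.

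For the second group that means exit on 5 of the 9 permitted EOS days, with the December exception in step 2. This rests on study exit meaning the EOS visit. The number of year-only starts is not given, so the number of affected records cannot be estimated. The effect is confined to descriptive medication classification; the adverse event, laboratory, vital sign and ECG summaries do not use this rule. It is worth correcting because the error is clear and cheap to remove.

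**What to change.** Replace the year-only bullet in SAP 5.2.2.3 with three conditions:

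1. Impute 1 January of the recorded year, or the first dose date if it falls in that year, whichever is later.
2. As an exception, treat the drug as started before first dose if its recorded end date precedes first dose or if it is recorded as ongoing at Day 1.
3. Never impute a start later than the recorded end date.

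Conditions 2 and 3 are needed because condition 1 alone leaves the drug in step 4 of the working misclassified.

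The cost is a line of SAP text and the matching code. The downside is that a few more drugs are classed as concomitant, for example one taken before first dose that has no end date and is not recorded as ongoing at Day 1. In a safety study that is the more cautious error. If the plan is already final, SAP Section 1 provides for substantive changes to be identified in the CSR.
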